9.4	Outcomes	14
9.4.1	Primary outcome	Error! Bookmark not defined.
9.4.2	Secondary outcomes	Error! Bookmark not defined.
9.5	Data Analyses	Error! Bookmark not defined.
10	DATA COLLECTION AND QUALITY ASSURANCE	14
10.1	Data Collection Forms	14

10.2	Data Management	14
10.3	Quality Assurance	15
10.3.1	Training	15
10.3.2	Quality Control Committee.....	Error! Bookmark not defined.
10.3.3	Metrics	15
10.3.4	Protocol Deviations.....	15
10.3.5	Monitoring	15
11	PARTICIPANT RIGHTS AND CONFIDENTIALITY	15
11.1	Institutional Review Board (IRB) Review	15
11.2	Informed Consent Forms	15
11.3	Participant Confidentiality	16
11.4	Study Discontinuation.....	16
12	ETHICAL CONSIDERATIONS.....	16
13	COMMITTEES.....	Error! Bookmark not defined.
14	PUBLICATION OF RESEARCH FINDINGS	16
15	REFERENCES.....	17
16	SUPPLEMENTS/APPENDICES	17

I. Procedures Schedule

II. Informed Consent Form Template

III. Other (add as many appendices as necessary)

PRÉCIS

Study Title

Patient Priorities Care for Hispanics with Dementia: adaptation and feasibility pilot study

Objectives

Primary Objective: Adapt the Patient Priorities Care (PPC) approach (<https://patientprioritiescare.org/>) for Hispanics with multiple chronic conditions (MCC) and dementia.

Secondary Objective: Test feasibility of implementation of PPC in a sample of older Hispanics with MCC and dementia cared for at a Geriatrics Outpatient Clinic.

Design and Outcomes

Patient priorities care (PPC) will be initially incorporated in the workflow of a Geriatrics outpatient clinic at The University of Texas Medical Branch (UTMB). The PPC approach will be culturally adapted for older Hispanics in Texas through pilot testing with 5 subjects (Hispanics with multiple chronic conditions (MCC) and normal cognition). The study team will make clarifying edits to materials and processes to finalize adaptations to the 6-step toolkit for conducting PPC with Hispanics. Once the PPC team and the advisory team have completed all changes, a feasibility study with 20 Hispanics with cognitive impairment will be conducted in the same clinic at UTMB.

The primary objective of this pilot proposal is to adapt PPC for Hispanics. A secondary objective is to test the feasibility of using it on Hispanics with dementia. We will thus adapt and test PPC with 5 Hispanics and then test the adapted version with 20 Hispanics with dementia. One exploratory outcome is to determine if primary care providers use the identified priorities in the electronic medical record to guide changes in care aligned with priorities. The degree of alignment of care with priorities will be analyzed through chart reviews.

Interventions and Duration

Each participant will have one priority setting session with a PPC facilitator and one care alignment session with their PCP and will then have 1 interview with a research team member to evaluate the intervention.

Sample Size and Population

This pilot project is not intended to identify specific outcomes resulting from the PPC approach, thus no power calculations are needed. We will use descriptive statistics to examine frequency distributions and proportions for all quantitative variables. We will calculate effect sizes for changes in our exploratory outcome. Interviews with practice-based implementation team members will be performed by [name] and analyzed using directed content analysis. Quantitative and qualitative findings will be triangulated using standard content

analysis methods to create meta-themes that synthesize the quantitative and qualitative findings. Inclusion of 20 subjects is therefore sufficient to directed content analysis with the expectation that we will obtain data saturation of each content area.

STUDY TEAM ROSTER

Principal Investigator: **[name]**

[name]
[name]
[name]
[contact]
[contact]

Role: PPC Content expert. He will oversee all research activities at UTMB and conduct quality control activities to make sure that adaptation and implementation of the PPC approach is done appropriately.

Co-Investigators: **[name] PhD**

[name]
[name]
[name]
[contact]
[contact]

Role: He will oversee implementation of the study at UTMB and will serve as the facilitator for all priority setting encounters in the study.

Research Coordinator: **[name], MS**

[name]
[name]
[name]
[contact]
[contact]

PARTICIPATING STUDY SITES

Site Principal Investigator: **[name] PhD**

The University of Texas Medical Branch
Geriatrics Clinic

2 STUDY OBJECTIVES

2.1 Primary Objective

Adapt PPC to be culturally appropriate for Hispanics with dementia and test its feasibility in an outpatient setting.

2.2 Secondary Objectives

The adapted version of PPC will improve care by identifying the healthcare priorities of Hispanics with dementia and aligning them with the care they receive.

3 BACKGROUND AND RATIONALE

3.1 Background on Condition, Disease, or Other Primary Study Focus

Most older adults with dementia have multiple chronic conditions (MCC),^{1,2} experience difficulty managing their MCC, and have poorer outcomes.³⁻⁶ Managing MCC typically involves adhering to single-disease clinical practice guidelines (CPG). This approach often results in burdensome care with outcomes that may not reflect what matters most to patients.⁷⁻¹⁰ To address the challenges for caring for patients with MCC, we developed Patient Priorities Care (PPC) – an approach that aligns disease management with patient priorities rather than CPG, to improve care.¹⁰⁻¹³ We demonstrated feasibility and effectiveness of PPC in a study embedded within a large primary and specialty care network.¹⁴ Patients reported less burdensome treatment and had fewer medications and referrals.¹⁴ A subsequent study found that PPC helped clinicians recommend home and community services aligned with patient priorities.¹⁵ Focusing on patient priorities rather than CPG is a patient-centered approach that integrates well in routine clinic encounters.¹⁶

3.2 Study Rationale

Physical, emotional, and cognitive impairments related to dementia interfere with disease self-management.¹⁷ Persons living with dementia (PlwD) therefore rely on caregivers for care and decision-making. Caregivers may add complexity to the patient-clinician interaction but are essential for translating ‘what matters most’ for PlwD into healthcare decisions.¹⁸ Patient and caregiver involvement should include identifying outcome goals and care preferences (health priorities) as well as aligning care to meet those priorities. It is therefore important to integrate caregivers into the healthcare process to achieve high-quality, family-centered care.^{19,20} In a feasibility study among Veterans with cognitive impairment and their caregivers, we demonstrated that PlwD and their caregivers are willing and able to identify health priorities. Clinicians could align care to achieve these priorities when placed in the electronic health record (EHR).

PlwD from minority groups experience more difficulties and poorer outcomes compared to their Non-Hispanic White (NHW) counterparts.³⁻⁶ Hispanics are the fastest growing underrepresented population in the USA, and have 1.5 times higher risk of dementia compared to NHW.²¹ Hispanics rely heavily on their families and there is a cultural

expectation of families to provide care to members in need.^{22,23} Recent data report older Hispanics prefer care at home rather than professional care.²⁴ Cultural differences and language barriers play key roles in shaping healthcare priorities and how priorities impact outcomes among Hispanics.²⁵

4 **STUDY DESIGN**

Figure 1. Conceptual Model of the Patient Priorities Care Approach

[figure not shown]

Figure 1 presents the main conceptual model of the PPC approach. For the adaptation 5 Hispanic patients will be included and for the feasibility test 20 Hispanic patients with cognitive impairment will be included.

The process will be as follows:

- 1) Eligible Hispanic patients will be identified through the patient roster of the Geriatrics Outpatient Clinic at UTMB.
- 2) Primary care providers will be asked to select patients they believe would not be good candidates for the study.
- 3) A research team member will contact the eligible patients and invite them to schedule the priority setting appointment (Step One). For those that agree she will obtain assent and/or consent and schedule the session.
- 4) The day of the session, the facilitator will use the PPC materials and identify the patient priorities and document them in the electronic health record. The visit will be audio recorded.
- 5) A research team member will schedule an appointment with the patient's primary care provider (PCP) within 2 weeks to conduct the alignment portion of the PPC approach (Steps two).
- 6) The primary care provider will discuss the patient priorities and the provider will align care to meet those priorities and document changes in care based on the discussion on the electronic health record (Step 3).
- 7) A research member will call the patient and assess their satisfaction with the PPC

approach 2 weeks after the visit with the primary care provider.

- 8) A research member will contact the primary care provider and assess their satisfaction with the PPC approach.
- 9) The PI, Co-PI and advisory team will review all the information and make adjustments to the protocol for the feasibility phase.
- 10) Steps 1-8 will be repeated with 20 Hispanic patients with dementia to test feasibility of the adapted PPC approach for Hispanics.

5 SELECTION AND ENROLLMENT OF PARTICIPANTS

The study has an initial adaptation phase and then a feasibility testing phase. For the adaptation phase 5 Hispanics with multiple chronic condition and without dementia will be invited to participate. These participants will need to consent to be part of the study. For the second phase, dementia can affect ability to consent. Thus, we will determine if participants with dementia have capacity by asking their primary care providers or by administering the telephone version of the Montreal Cognitive Assessment. If a score of less than 12 is obtained, the caregiver will be asked to consent for both participants.

5.1 Inclusion Criteria

For adaptation group (n=5)

- Patient's primary care provider is located in the UTMB Geriatrics Outpatient Clinic in Galveston.
- Patient identifies as Hispanic.
- Patient speaks English or Spanish.
- Patient has multiple chronic conditions listed as diagnoses in their electronic health record (3 or more chronic conditions).
- Consent to participate in all parts of the study.
- Primary care provider agrees with participation.

For feasibility testing (n=20)

- Patient's primary care provider is located in the UTMB Geriatrics Outpatient Clinic in Galveston.
- Patient identifies as Hispanic.
- Patient speaks English or Spanish.
- Patient has multiple chronic conditions listed as diagnoses in their electronic health record (3 or more chronic conditions).
- Patient has diagnosis of dementia.
- Have a caregiver willing to provide consent.

- Patient consent if he/she has capacity as deemed by their primary care provider or assent if he/she doesn't have capacity.

5.2 Exclusion Criteria

For adaptation group (n=5)

- Patient's primary care provider located at UTMB but not in the Geriatrics Outpatient Clinic.
- Non-Hispanic patients.
- Speaks language other than English or Spanish.
- Patient does not have multiple chronic conditions.
- Deemed ineligible by primary care provider.
- Patient has diagnosis of dementia.

For feasibility testing (n=20)

- Patient's primary care provider located at UTMB but not in the Geriatrics Outpatient Clinic.
- Non-Hispanic patients.
- Speaks language other than English or Spanish.
- Patient does not have multiple chronic conditions.
- Patient doesn't have diagnosis of dementia.
- Patient deemed ineligible by primary care provider.
- Patient doesn't provide consent or assent based on capacity.
- Caregiver doesn't provide consent.

5.3 Study Enrollment Procedures

The electronic health record at UTMB allows for selection of patients with different conditions that are cared for at specific clinics. For the adaptation part of the study we will select a list of Hispanics cared for at the UTMB Geriatrics Outpatient Clinic and ask primary care providers to exclude those that are not eligible for the study. For the feasibility part we will select Hispanic patients cared for at the UTMB Geriatrics Outpatient Clinic that are part of the dementia registry

in the electronic health record and have MCC. We will then ask their primary care providers to exclude those not eligible for the study.

6 STUDY INTERVENTIONS

6.1 Interventions, Administration, and Duration

For Step One of the PPC approach the priority setting session will take on average between 40-minutes and 60 minutes. Priority setting requires discussion of the patient's priorities and identifying what they are and are not willing to do to reach those priorities. Minimal risk is expected at this visit other than feeling uncomfortable with discussing their health related problems given that this is part of usual care.

7 STUDY PROCEDURES

Two clinic visits and one telephone follow-up comprise the entire intervention.

7.1 Description of Evaluations

7.1.1 Screening Evaluation

Consenting Procedure

Potential participants will be contacted over the phone by the research coordinator who will explain the project. A script will be available on Redcap for consent. Consenting will be performed once over the phone and verbal consent will be documented on the form. If the patient is deemed unable to consent in the pre-screening phase by the PCP or if they obtain a score less than 12 in the telephone version of the MoCA, a competent caregiver will be asked to consent and then the patient will provide assent.

Screening

The screening process will continue until all participants are included in the study.

7.1.2 Enrollment, Baseline, and/or Randomization

Enrollment

Enrollment will occur on the first visit where healthcare goals are identified.

Baseline Assessments

The visit where healthcare goals are identified is considered the baseline assessment.

Randomization

There will be no randomization.

7.1.3 Follow-up Visits

There will be one follow-up visit once healthcare goals are identified to conduct care alignment with the PCP. Once this step is completed there will be 1 follow-up call to evaluate the PPC process.

7.1.4 Completion/Final Evaluation

The care alignment visit is considered the final visit.

8 **SAFETY ASSESSMENTS**

A participant is enrolled if he/she completes the care alignment visit. No adverse events are expected given that only goal setting and care alignment will be performed as part of routine clinical visits.

8.1 Specification of Safety Parameters

We will monitor charts of enrolled subjects to track for any adverse events related to changes in care arising from care alignment procedures that differ from routine guidelines.

8.2 Methods and Timing for Assessing, Recording, and Analyzing Safety Parameters

The proposed studies builds from prior published studies (Tinetti et al. JAMA Int Med 2019 and Freytag et al. JAGS 2020) using the Patient Priorities Care approach. These studies did not identify any significant AEs or SAEs related to the study protocols. Chart reviewers analyzed changes in care related to care alignment and attempted to attribute those care changes to any noted adverse events. No significant AEs or SAEs were identified.

8.3 Adverse Events and Serious Adverse Events

Adverse Event (AE): We will review charts from any potential AEs including urgent care visits, emergency department or hospital stays occurring after the care alignment step of PPC.

Serious Adverse Event (SAE): The intervention will not result in any of the following events, thus no SAE are expected. If a death occurs while the study participant is actively in the study this will be reported within 48 hours of occurrence or as soon as the study team finds out about the event.

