8.3.1 Follow-up for Adverse Events

[name] or [name] will record all reportable events with start dates occurring any time after informed consent is obtained until 7 (for non-serious AEs) or 30 days (for SAEs) after the last day of study participation. At each study visit, the investigators will inquire about the occurrence of AE/SAEs since the last visit. Events will be followed for outcome information until resolution or stabilization.

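### As written, participants are not asked about adverse events after care has changed, and how long a later admission is recorded depends on a label that 8.3 does not settle

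*Combined protocol and SAP*

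**What the plan says.** Active inquiry is set in Section 8.3.1: "At each study visit, the investigators will inquire about the occurrence of AE/SAEs since the last visit". The schedule is set in three places. Section 7 says "Two clinic visits and one telephone follow-up comprise the entire intervention". Section 7.1.3 gives one follow-up visit for care alignment and then, separately, one call to evaluate the process. Section 7.1.4 says "The care alignment visit is considered the final visit". Item 7 of the process list in Section 4 gives the purpose of the call, 2 weeks after the visit to the primary care provider: "A research member will call the patient and assess their satisfaction with the PPC" approach.

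On classification, the AE paragraph of 8.3 has charts reviewed for "any potential AEs including urgent care visits, emergency department or hospital stays occurring after the care alignment step of PPC". Metrics (numbered 10.3.2, within Section 11.3) also lists hospital admissions as adverse events. The SAE paragraph of 8.3 reads "The intervention will not result in any of the following events, thus no SAE are expected". No list follows; the next sentence deals only with death: "If a death occurs while the study participant is actively in the study this will be reported within 48 hours of occurrence", or when the team learns of it.

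Section 8.3.1 then sets the recording period by seriousness, from informed consent "until 7 (for non-serious AEs) or 30 days (for SAEs) after the last day of study participation". That last day is not defined.

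**The concern.** Care changes at the alignment visit. An admission that follows such a change is the kind of event that 8.1 sets out to track. The inquiry rule looks back from each visit to the one before, so the question asked at alignment covers the time before any care has changed. After that visit the plan schedules no further study visit. Knowledge of later events then rests on charts alone, although a conversation with the participant is already booked for 2 weeks later.

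The second part concerns counting. The recording period depends on whether an event is serious, and 8.3 does not say whether an admission is. Two careful readers could enter the same admission differently, or one could leave it out. The pilot's AE and SAE counts would then partly reflect the reader.

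**Working it through.** **1. When is a participant asked?** Taking the sections in time order:

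- Priority-setting session: a visit; the AE question applies.
- Care alignment visit: the final visit (7.1.4); the question covers the interval since the session. Care changes here (Section 4, item 6).
- Call 2 weeks later: Section 7 counts it apart from the two clinic visits, and 7.1.3 counts it apart from the single follow-up visit. Its stated content is satisfaction (Section 4, item 7) or evaluation of the process (7.1.3).

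The inquiry therefore ends at alignment. The chart review in 8.3 and 10.3.2 covers the time after it. The two sources do not overlap in the period that matters.

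**2. How long is an admission recorded?** The plan states only the offsets, 7 and 30 days (8.3.1). It gives no calendar limit to reproduce. Let day 0 be the alignment visit, and assume that the call falls exactly on day 14. Limit = last day of participation + offset.

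| Last day taken as | Non-serious AE | SAE | Gap |
|---|---|---|---|
| Alignment visit (7.1.4) | 0 + 7 = day 7 | 0 + 30 = day 30 | 23 days |
| Call (Section 7; Section 4, item 7) | 14 + 7 = day 21 | 14 + 30 = day 44 | 23 days |

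The choice of last day moves each limit by 14 days. The label moves it by 30 − 7 = 23 days in both rows.

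Take an admission on day 25. As a non-serious AE it is too late in both rows (25 > 7 and 25 > 21). As an SAE it is in time in both (25 < 30 and 25 < 44). From day 22 to day 30 the label alone decides, whichever last day is used.

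**3. Scale.** If all planned participants complete alignment, the label-dependent time is 25 × 23 = 575 person-days, of which 20 × 23 = 460 belong to the dementia group. I do not give this as a share of the recording period, because recording starts at consent and the documents do not fix the time from consent to alignment.

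The documents give no admission rate. Purely as an illustration, assume 0.3 to 1.0 admissions per person-year. Then 575 / 365.25 = 1.57 person-years, and 1.57 × 0.3 to 1.57 × 1.0 gives about 0.5 to 1.6 admissions whose recording depends on the label. Neither finding rests on this assumed rate.

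**The case against.** The case on the other side has four parts.

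- **The call may count as a visit.** Section 7.1.3, which mentions it, is headed as follow-up visits, and Section 4 does not say that the call covers nothing but satisfaction. This leaves some ambiguity. But the text under that heading separates the one visit from the one call, and 7.1.4 closes the sequence of visits at alignment, so the natural reading stands.
- **The SAE criteria may exist elsewhere.** Section 8.4 refers to NIA guidelines and to a data safety monitoring plan that is not reproduced here, and a list in 8.3 could have been lost from the text. A reader might infer that the study has no SAE definition. The documents support only that 8.3 shows none and does not point to one.
- **Charts are reviewed anyway.** Metrics (10.3.2) covers all enrolled subjects, with an attribution review for each event. Monitoring (10.3.4) adds monthly reviews, and the IRB is told of AEs that stem from a care change. None of this depends on seriousness or has an end date. A reader might infer that admissions will go undetected; the documents do not support that. What remains is that charts are the only planned source after alignment, and the documents do not say whether they show care received elsewhere.
- **The limits are not fixed at days 21 and 44.** That pair needs the call to be the last day. Section 7 supports this by counting the call in the intervention, but 7.1.4 points to days 7 and 30. Only the 23-day gap holds under both readings.

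**Conclusion.** The point holds as a modest one that is cheap to correct. On the natural reading, no AE question is scheduled after the visit at which care changes. Separately, an admission is recorded to day 7 or 21 as a non-serious AE, or to day 30 or 44 as an SAE, and 8.3 does not settle which applies.

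The consequence is less complete capture and inconsistent recording of events after alignment. It does not reach the feasibility outcomes. A reader might take the opening of the SAE paragraph to mean that the plan ignores harm. It is worded more firmly than 8.2 supports, since 8.2 reports only that earlier studies identified no significant events, but 8.1 does monitor for events from care changes that depart from usual guidelines.

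The conclusion assumes that the call is not a study visit, that it takes place on day 14, and that the unseen monitoring plan does not already settle the classification. If that plan does, the missing question and the undefined last day remain.

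**What to change.** 1. Add an AE/SAE question to the 2-week call, asking by name about urgent care, emergency department and hospital use since the alignment visit.
2. In 8.3, state that hospital admissions are SAEs, or cite the monitoring plan if it already says so.
3. In 8.3.1, define the last day of participation as the call, so that admissions are recorded at least to 30 days after it (day 44 when the call is on day 14). Word this as a minimum: the chart review now has no end date and should not be shortened.

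The cost is one question in the call script and a short edit to each of two sections. The downside is that some unrelated admissions will be recorded and will need the attribution review that 10.3.2 already requires. At the same assumed rates, 25 × 44 = 1,100 person-days, or 1,100 / 365.25 = 3.01 person-years, gives about 0.9 to 3.0 admissions in total by day 44.
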